‡ Other types of cognitive impairment included mild cognitive impairment, Parkinson's disease dementia, mixed dementia, etc.

Table 2. Between-group comparison in outcomes versus CAU group

Outcomes	CAT vs. Routine care		CAE vs. Routine care		CAT+CAE vs. Routine care	
	Difference (95% CI)	P value [‡]	Difference (95% CI)	P value [‡]	Difference (95% CI)	P value [‡]
Primary outcome						
MoCA *						
Week-6	XX (XX, XX)	XX	XX (XX, XX)	XX	XX (XX, XX)	XX
Week-12	XX (XX, XX)	XX	XX (XX, XX)	XX	XX (XX, XX)	XX
Secondary outcomes						
DSF *						
Week-6	XX (XX, XX)	XX	XX (XX, XX)	XX	XX (XX, XX)	XX
Week-12	XX (XX, XX)	XX	XX (XX, XX)	XX	XX (XX, XX)	XX
DSR *						
Week-6	XX (XX, XX)	XX	XX (XX, XX)	XX	XX (XX, XX)	XX
Week-12	XX (XX, XX)	XX	XX (XX, XX)	XX	XX (XX, XX)	XX
MBI *						
Week-6	XX (XX, XX)	XX	XX (XX, XX)	XX	XX (XX, XX)	XX
Week-12	XX (XX, XX)	XX	XX (XX, XX)	XX	XX (XX, XX)	XX
VAS †						
Week-6	XX (XX, XX)	XX	XX (XX, XX)	XX	XX (XX, XX)	XX
Week-12	XX (XX, XX)	XX	XX (XX, XX)	XX	XX (XX, XX)	XX
GDS †						
Week-6	XX (XX, XX)	XX	XX (XX, XX)	XX	XX (XX, XX)	XX
Week-12	XX (XX, XX)	XX	XX (XX, XX)	XX	XX (XX, XX)	XX
ISI †						
Week-6	XX (XX, XX)	XX	XX (XX, XX)	XX	XX (XX, XX)	XX
Week-12	XX (XX, XX)	XX	XX (XX, XX)	XX	XX (XX, XX)	XX
Outcomes	CAT+CAE vs. CAT		CAT+CAE vs. CAE		CAT vs. CAE	
	Difference (95% CI)	P value [‡]	Difference (95% CI)	P value [‡]	Difference (95% CI)	P value [‡]
Primary outcome						
MoCA *						
Week-6	XX (XX, XX)	XX	XX (XX, XX)	XX	XX (XX, XX)	XX
Week-12	XX (XX, XX)	XX	XX (XX, XX)	XX	XX (XX, XX)	XX
Secondary outcomes						
DSF *						
Week-6	XX (XX, XX)	XX	XX (XX, XX)	XX	XX (XX, XX)	XX
Week-12	XX (XX, XX)	XX	XX (XX, XX)	XX	XX (XX, XX)	XX
DSR *						
Week-6	XX (XX, XX)	XX	XX (XX, XX)	XX	XX (XX, XX)	XX
Week-12	XX (XX, XX)	XX	XX (XX, XX)	XX	XX (XX, XX)	XX
MBI *						
Week-6	XX (XX, XX)	XX	XX (XX, XX)	XX	XX (XX, XX)	XX
Week-12	XX (XX, XX)	XX	XX (XX, XX)	XX	XX (XX, XX)	XX
VAS †						
Week-6	XX (XX, XX)	XX	XX (XX, XX)	XX	XX (XX, XX)	XX
Week-12	XX (XX, XX)	XX	XX (XX, XX)	XX	XX (XX, XX)	XX
GDS †						
Week-6	XX (XX, XX)	XX	XX (XX, XX)	XX	XX (XX, XX)	XX
Week-12	XX (XX, XX)	XX	XX (XX, XX)	XX	XX (XX, XX)	XX
ISI †						
Week-6	XX (XX, XX)	XX	XX (XX, XX)	XX	XX (XX, XX)	XX
Week-12	XX (XX, XX)	XX	XX (XX, XX)	XX	XX (XX, XX)	XX

Abbreviations: CAT, comprehensive acupuncture therapy; CAE, Comfy Acupressure for the Elderly; DSF, Digit Span Forward; DSR, Digit Span Reverse; GDS, Geriatric Depression Scale; ISI, Insomnia Severity Index; MBI, Modified Barthel Index; MoCA, Montreal Cognitive Assessment; VAS, Visual Analogue Scale.

* A greater positive value represents improvement in symptoms.

† A greater negative value represents improvement in symptoms.

‡ *P* value was calculated using a mixed-effects model with baseline adjustment to illustrate between-group differences. Those which statistical differences $p<0.05$ reached significance level are indicated in bold font.

Table 3. Intra-group comparison in outcomes

Outcomes	Change from baseline							
	CAT (n=62)		CAE (n=62)		CAT+CAE (n=62)		Routine care (n=62)	
	Mean (95%CI)	P value [‡]	Mean (95%CI)	P value [‡]	Mean (95%CI)	P value [‡]	Mean (95%CI)	P value [‡]
Primary outcome								
MoCA *								
Week-6	XX (XX, XX)	XX	XX (XX, XX)	XX	XX (XX, XX)	XX	XX (XX, XX)	XX
Week-12	XX (XX, XX)	XX	XX (XX, XX)	XX	XX (XX, XX)	XX	XX (XX, XX)	XX
Secondary outcomes								
DSF *								
Week-6	XX (XX, XX)	XX	XX (XX, XX)	XX	XX (XX, XX)	XX	XX (XX, XX)	XX
Week-12	XX (XX, XX)	XX	XX (XX, XX)	XX	XX (XX, XX)	XX	XX (XX, XX)	XX
DSR *								
Week-6	XX (XX, XX)	XX	XX (XX, XX)	XX	XX (XX, XX)	XX	XX (XX, XX)	XX
Week-12	XX (XX, XX)	XX	XX (XX, XX)	XX	XX (XX, XX)	XX	XX (XX, XX)	XX
MBI *								
Week-6	XX (XX, XX)	XX	XX (XX, XX)	XX	XX (XX, XX)	XX	XX (XX, XX)	XX
Week-12	XX (XX, XX)	XX	XX (XX, XX)	XX	XX (XX, XX)	XX	XX (XX, XX)	XX
VAS †								
Week-6	XX (XX, XX)	XX	XX (XX, XX)	XX	XX (XX, XX)	XX	XX (XX, XX)	XX
Week-12	XX (XX, XX)	XX	XX (XX, XX)	XX	XX (XX, XX)	XX	XX (XX, XX)	XX
GDS †								
Week-6	XX (XX, XX)	XX	XX (XX, XX)	XX	XX (XX, XX)	XX	XX (XX, XX)	XX
Week-12	XX (XX, XX)	XX	XX (XX, XX)	XX	XX (XX, XX)	XX	XX (XX, XX)	XX
ISI †								
Week-6	XX (XX, XX)	XX	XX (XX, XX)	XX	XX (XX, XX)	XX	XX (XX, XX)	XX
Week-12	XX (XX, XX)	XX	XX (XX, XX)	XX	XX (XX, XX)	XX	XX (XX, XX)	XX

Abbreviations: CAT, comprehensive acupuncture therapy; CAE, Comfy Acupressure for the Elderly; DSF, Digit Span Forward; DSR, Digit Span Reverse; GDS, Geriatric Depression Scale; ISI, Insomnia Severity Index; MBI, Modified Barthel Index; MoCA, Montreal Cognitive Assessment; VAS, Visual Analogue Scale.

* A greater positive value represents improvement in symptoms.

† A greater negative value represents improvement in symptoms.

‡ P value was calculated using a mixed-effects model with baseline adjustment to illustrate pre- and post-treatment within-group differences. Those which statistical differences $p<0.05$ reached significance level are indicated in bold font

Table 4. Adverse events related to treatment, n (%)^{*}

Adverse event	CAT (n = 62)	CAE (n = 62)	CAT+CAE (n = 62)
Bleeding at the site of needling	XX (XX)	XX (XX)	XX (XX)
Hematoma around the site of needling	XX (XX)	XX (XX)	XX (XX)
Dizziness after treatment	XX (XX)	XX (XX)	XX (XX)
Headache after treatment	XX (XX)	XX (XX)	XX (XX)
Localized pain	XX (XX)	XX (XX)	XX (XX)
Needle phobia	XX (XX)	XX (XX)	XX (XX)

Abbreviations: CAT, comprehensive acupuncture therapy; CAE, Comfy Acupressure for the Elderly.

* Data was expressed as number of patients (%).

Table 5. Reported adverse events in different categories, n (%)^{*}

Adverse Event Category	CAT (n=62)	CAE (n=62)	CAT+CAE (n=62)	Routine care (n=62)	P-value*
Any	XX (XX)	XX (XX)	XX (XX)	XX (XX)	XX
Mild	XX (XX)	XX (XX)	XX (XX)	XX (XX)	XX
Moderate	XX (XX)	XX (XX)	XX (XX)	XX (XX)	XX
Severe	XX (XX)	XX (XX)	XX (XX)	XX (XX)	XX
Life-threatening	XX (XX)	XX (XX)	XX (XX)	XX (XX)	XX
Death	XX (XX)	XX (XX)	XX (XX)	XX (XX)	XX

Abbreviations: CAT, comprehensive acupuncture therapy; CAE, Comfy Acupressure for the Elderly.

* Data was expressed as number of patients (%). Those which statistical differences $p < 0.05$ reached significance level are indicated in bold font.

[figure not shown]

Figure 1. CONSORT Flowchart

References

1. American Psychiatric Pub. Diagnostic and Statistical Manual of Mental Disorders (DSM-5®). American Psychiatric Pub; 2013.

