- (b) to determine whether other symptoms (e.g., functional independence, pain, depression, and sleep disorder) in the treatment group improve more than in the control group; and
- (c) to investigate whether acupuncture or acupressure is safe for the elderly with cognitive impairment or dementia.

Patient population

Elderly patients with cognitive impairment or dementia are eligible for enrolment.

Inclusion criteria

Subjects will be eligible for this study if they:

- (a) are aged 65 years or above;

- (b) have a clinical diagnosis of any type of dementia or met the criteria of major and mild neurocognitive disorder based on the Fifth Edition of the Diagnostic and Statistical Manual of Mental Disorders (DSM-5);¹ and
- (c) have mild to moderate dementia at a stage of 3 to 5 on the Global Deterioration Scale.²

Exclusion criteria

Subjects will be excluded if they:

- (a) have the severity of dementia with a stage below 3 or above 5 on the Global Deterioration Scale;
- (b) have severe skin lesions on acupuncture and acupressure areas;
- (c) have a significant bleeding tendency;
- (d) have a heart pacemaker or implantable cardioverter defibrillator;
- (e) are currently receiving acupressure as a regular therapy;
- (f) have had surgery on the head or neck; or
- (g) are currently receiving anti-coagulant treatment.

Randomization, central allocation and blindness

One independent research assistant will be in charge of randomization and central allocation as the central coordinator. After confirmation of patients' eligibility and completion of the baseline assessment, participants will be randomly assigned to CAT, CAE, CAT+CAE, or routine care groups in a ratio of 1:1:1:1. Random codes were produced in advance using simple, complete, non-sequential numbers, with a block of 4, 8 and 12, through a random allocation software at <http://mahmoodsaghaei.tripod.com/Softwares/randalloc.html>. Randomization information will be sealed in sequentially numbered opaque envelopes.

Central allocation will be conducted, i.e., site investigators who are responsible for subjects' eligibility will obtain the opaque envelope from the central coordinator for an eligible subject who will be allocated to one of the four groups. Each envelope will be opened by acupuncturists after the participant completes the baseline assessment. Clinical assessors and data analysts will be blind to patients' treatment.

Intervention

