Our recent study showed that CAT treatment for 8 weeks produced a 2.3 ± 2.8 (SD) score greater improvement than control (minimum acupuncture stimulation, MAS) on MoCA in patients with poststroke cognitive impairment.¹³ One similar trial has reported that acupuncture treatment alone for 3 months yielded a 1.9 ± 4.1 greater improvement than nimodipine, a commonly used anti-hypertension drug, on MoCA in patients with poststroke cognitive impairment.¹⁴ Based on these two trials, we expect that CAT could yield an average 2.1 [$(2.3+1.9)/2 = 2.1$] score greater improvement on MoCA than routine care, with an average standard deviation (SD) equal to a 1.7-fold of mean difference [$(2.8/2.3 + 4.1/1.9)/2 = 1.7$], i.e., $SD = 1.7 \times 2.1 = 3.6$. The following formula is then used to further calculate the sample size:

$$n = \frac{2}{(M/SD)^2} \times C_{p,\text{power}}$$

where n is the number of subjects required in each arm and M is the mean difference that is equal to 2.1. SD is the standard deviation that is 3.6. $C_{p,\text{power}}$ is equal to 7.9 when the two-tailed level of α and power ($1-\beta$) are set at 0.05 and 80%, respectively. It requires 62 subjects per arm, with an assumed dropout rate of 25%. We propose to recruit a total of 248 subjects ($n = 62$ per arm for 4 arms).

Data processing and analysis

General principles

One biostatistician who is blinded to interventions will be responsible for statistical analysis. The analysis will be carried out on the intention-to-treat (ITT) population. For all primary and secondary outcomes, two-tailed P-values will be reported in addition to confidence intervals. The nominal level of statistical significance (α) will be 5%. The analysis and reporting of the results will follow the Consolidated Standards of Reporting Trials (CONSORT) guidelines.

Analysis software

All analyses will be performed using R Studio version 4.0.0 or later.

Analysis Populations

All analyses will be carried out on the intention-to-treat (ITT) population, for which participants have been randomized, completed the baseline assessment regardless of protocol compliance.¹⁵ The flow of patients throughout the trial will be shown using a CONSORT diagram (Figure 1).

Demographic characteristics and baseline comparisons

Baseline comparisons will be tabulated for the following variables (Proposed Table 1):

- (a) Age
- (b) Gender (Categories: male / female)

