- (c) Marital status (Categories: married or living with partner / single, separated, divorced, or widowed)
- (d) Education level (Categories: uneducated / primary or below / lower secondary / upper secondary / university or above)
- (e) Past occupation (Categories: managers and administrators / professional and associate professional / skilled and semi-skilled worker / unskilled worker / housework / others)
- (f) Type of cognitive impairment (Categories: Alzheimer's disease / vascular dementia / others)
- (g) Past medical history (Categories: cardiometabolic disease / malignant neoplasm / stroke / Parkinson's disease / psychotic disorder / affective disorder)
- (h) Current medication (Categories: cholinesterase inhibitors / glutamate regulators / antidepressants / antipsychotics / hypnotics)

- (i) Baseline MoCA score
- (j) Baseline DSF and DSR scores
- (k) Baseline MBI score
- (l) Baseline VAS score
- (m) Baseline GDS-15 score
- (n) Baseline ISI score

Continuous variables will be presented using mean with standard deviation (SD). One-way analysis of variance (one-way ANOVA) will be used to detect differences in continuous baseline variables.

Categorical variables will be presented by counts with percentages. Percentages will be calculated according to the number of patients for whom data are available. Categorical variables will be analyzed using the Chi-square test or Fisher's exact test.

Discontinuation will be summarized by counts with percentages. Chi-square test or Fisher's exact test will be used to detect differences between the four groups.

Primary outcome

A linear mixed-effect model will be applied to compare the primary outcome (changes in total MoCA score from baseline), with time (baseline, week 6, and week 12) and group (CAT, CAE, CAT+CAE, and routine care) as categorical fixed factors and random intercepts within a scaled identity covariance matrix. Gender, age, baseline MoCA score, and baseline medication will serve as covariates. Pairwise comparisons will be further carried out to examine between-group differences. Two-tailed P-values will be reported in addition to confidence intervals ([Proposed Tables 2 and 3](#)).

Subgroup analysis will be further conducted to compare outcomes to detect whether these subgroup factors are associated with outcomes. The following subgroups include:

- (a) Age (<85 years and \geq 85 years);
- (b) Gender (male and female); and

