- (c) severity of dementia (mild cognitive decline [Stage 3], moderate cognitive decline [Stage 4], moderately severe cognitive decline [Stage 5])

Secondary outcomes

A linear mixed-effect model will be applied to compare the secondary outcomes, including changes in scores of the Digit span test (DSF and DSR), MBI, VAS, GDS and ISI, with time (baseline, week 6, and week 12) and group (CAT, CAE, CAT+CAE, and routine care) as categorical fixed factors and random intercepts within a scaled identity covariance matrix. Gender, age, baseline MoCA score, and baseline medication will serve as covariates.

Pairwise comparisons will be further carried out to examine between-group differences. Two-tailed P-values will be reported in addition to confidence intervals ([Proposed Tables 2 and 3](#)).

Safety outcomes

AEs related to treatment will be tabulated by treatment group without statistical tests or confidence intervals ([Proposed Table 4](#)).

All AEs that occurred throughout the trial will be tabulated by treatment group and AE category (mild, moderate, severe, life-threatening, or death). Chi-square test or Fisher's exact test will be used to detect differences between the four groups ([Proposed Table 5](#)).

Details of serious AEs and death cases will be summarized and listed in a separate table.

Interim analysis

No interim outcome analyses were done prior to the completion of the study to avoid assessment bias.

Missing data

A linear mixed-effect model will be conducted for all analyses of primary and secondary outcomes without imputation of missing data.¹⁶

Proposed Tables

Table 1. Baseline characteristics

Characteristic	CAT (n=62)	CAE (n=62)	CAT+CAE (n=62)	Routine care (n=62)	Total (n=248)	P value
Age, years *	XX ± XX	XX ± XX	XX ± XX	XX ± XX	XX ± XX	XX
Gender (Female) †	XX (XX)	XX (XX)	XX (XX)	XX (XX)	XX (XX)	XX
Marital status †						XX
Married or living with partner	XX (XX)	XX (XX)	XX (XX)	XX (XX)	XX (XX)	
Single, separated, divorced, or widowed	XX (XX)	XX (XX)	XX (XX)	XX (XX)	XX (XX)	
Education level †						XX
Uneducated	XX (XX)	XX (XX)	XX (XX)	XX (XX)	XX (XX)	
Primary or below	XX (XX)	XX (XX)	XX (XX)	XX (XX)	XX (XX)	
Lower Secondary	XX (XX)	XX (XX)	XX (XX)	XX (XX)	XX (XX)	
Upper Secondary	XX (XX)	XX (XX)	XX (XX)	XX (XX)	XX (XX)	
University or above	XX (XX)	XX (XX)	XX (XX)	XX (XX)	XX (XX)	
Past occupation †						XX
Managers and administrators	XX (XX)	XX (XX)	XX (XX)	XX (XX)	XX (XX)	

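### Table 4 divides treatment-related adverse events by everyone randomized and shows no exposure, so participants who never start, or leave early for other reasons, dilute the percentages by an unknown amount

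*SAP*

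**What the plan says.** SAP, Analysis Populations: "All analyses will be carried out on the intention-to-treat (ITT) population, for which participants have been randomized". The definition continues with "completed the baseline assessment regardless of protocol compliance". It does not require that any treatment was received. The baseline condition removes nobody, because under the SAP's randomization section "Each envelope will be opened by acupuncturists after the participant completes the baseline assessment".

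SAP, Safety outcomes, names no other population. It says "AEs related to treatment will be tabulated by treatment group without statistical tests or confidence intervals". The shell for Table 4, titled "Adverse events related to treatment, n" (%), is headed n = 62 for CAT, CAE and CAT+CAE, and its footnote reads "Data was expressed as number of patients" (%). Table 5, covering all AEs by severity category, has 62 in each of four arms and a Chi-square or Fisher test.

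The only rule on percentages is "Percentages will be calculated according to the number of patients for whom data are available". It sits under the baseline comparisons and does not set a safety denominator.

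No table of sessions received is planned. The protocol's Treatment procedure gives full courses of 24 CAT and 36 CAE sessions and provides for discontinuation on intolerance or hospitalization. The SAP's sample-size section states "It requires 62 subjects per arm, with an assumed dropout rate of 25"%.

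**The concern.** ITT keeps the efficacy comparison free of post-randomization selection. A percentage of treatment-related harm answers a different question: how often harm occurs among people who were treated. Someone who never has a session cannot have bleeding or a hematoma at a needling site, yet adds one to the Table 4 denominator. Someone who leaves after a few sessions for an unrelated reason counts the same as someone who completes 24, 36 or, in the combined arm, 24 + 36 = 60 sessions.

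Safety is aim (c) in the SAP and aim (3) in the protocol, and Table 4 is the main display of treatment-related harm. It carries no intervals or tests, so readers will rely on the raw percentages. Without a record of exposure beside them, a reader cannot tell a well-tolerated treatment from one that was little used.

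**Working it through.** **The denominator.** Inputs from the SAP's sample-size section: M = 2.1, SD = 3.6, constant 7.9, dropout 25%.

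- n = 2/(2.1/3.6)² × 7.9 = 46.43 per arm
- 46.43/(1 − 0.25) = 61.9, rounded up to 62

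The plan's 62 reproduces. It is the number randomized and already includes the allowance for dropout. The same 62 heads each column of Table 4.

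**Never-treated participants.** Let x be the number of patients with an event and k the number randomized to an active arm who receive no session.

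- ITT rate = x/62
- Treated-only rate = x/(62 − k)
- Ratio = (62 − k)/62

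The documents do not give k, so the table shows a range. The last row takes all of the assumed dropout as never treated (0.25 × 62 = 15.5, rounded to 16).

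| k | 62 − k | Ratio | x = 3 (ITT 4.8%) | x = 10 (ITT 16.1%) |
|---|---|---|---|---|
| 0 | 62 | 1.000 | 4.8% | 16.1% |
| 1 | 61 | 0.984 | 4.9% | 16.4% |
| 3 | 59 | 0.952 | 5.1% | 16.9% |
| 6 | 56 | 0.903 | 5.4% | 17.9% |
| 16 | 46 | 0.742 | 6.5% | 21.7% |

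Using 5% exactly, 62 × 0.95 = 58.9 and 3/58.9 = 5.1%. Using 15.5 rather than 16, the ceiling ratio is 46.5/62 = 0.75.

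**Partial exposure.** This is a separate mechanism and needs assumptions that the documents do not supply: a constant AE hazard over 12 weeks, and 25% leaving for reasons unrelated to AEs. With full-course risk p, hazard h = −ln(1 − p)/12 per week, and risk by week t of 1 − exp(−ht), the reported risk is 0.75p + 0.25 × (mean risk among leavers).

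| Full-course risk | Leave evenly over 12 weeks | All leave at week 3 | Never treated |
|---|---|---|---|
| 10% | 8.8% | 8.2% | 7.5% |
| 20% | 17.6% | 16.4% | 15.0% |

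For p = 20% and even leaving, the mean risk among leavers is 1 − 0.2/0.2231 = 10.4%, so the reported risk is 0.75 × 20% + 0.25 × 10.4% = 17.6%.

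An at-least-one-session denominator corrects the first mechanism only. A participant with two sessions stays in it as one full unit.

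**The case against.** The strongest reply is that the effect may be negligible. Allocation is opened only after the baseline assessment, acupuncture is given in the participant's own care home, and few people may fail to start. With k = 1, 10 affected patients move from 16.1% to 16.4%. Table 4 has no tests, so no planned inference changes. Discontinuation is already tabulated by arm, counts stand beside percentages, and serious AEs and deaths are listed separately. All of this stands and limits the size. None of it gives the number treated or the sessions received.

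Four stronger readings are tempting, and the documents do not support them.

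- **That ITT always lowers the rate.** A participant who stops because of an AE is already in the numerator for that event, since active arms are asked about AEs at every session. Counting someone under an arm whose treatment they did not receive can move a rate either way.
- **That rates are understated by 12.5% to 25%.** This turns the assumed dropout into lost exposure (even leaving gives mean exposure 0.75 + 0.25 × 0.5 = 87.5%). The 25% comes from the MoCA sample size, and nothing says when or why those people leave or how many sessions they miss. Someone absent only at week 12 may be nearly fully exposed. The lower bound is zero.
- **That the distortion is worst in the least tolerated arm.** Those who stop for intolerance will normally have had the event recorded. The dilution comes from never-starters and from those who leave for other reasons.
- **That Table 5 has the same fault and needs the same change.** Table 5 is a tested four-arm comparison. Dropping never-starters from the active arms alone would introduce one-sided selection after randomization. Active arms are also asked about AEs at each session and controls only at baseline, week 6 and week 12, which pushes that comparison the other way.

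**Conclusion.** The point holds for Table 4. The SAP as written applies the efficacy population to treatment-related harm and plans no exposure summary, so the percentages are diluted whenever someone assigned to an active arm never starts or leaves early for a reason other than an AE. The n = 62 headings belong to unfilled shells, but the rule covering all analyses makes that denominator binding.

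The size is unknown. For never-starters alone the reported rate lies between 1.00 and about 0.74 to 0.75 of the treated-only rate. The lower figure is a ceiling on the effect, reached only if every assumed dropout never had a session. The partial-exposure figures are illustrations under a constant hazard and leaving unrelated to AEs. This is a cheap improvement to the reporting of a stated aim. It does not affect the efficacy analysis.

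**What to change.** In the SAP, under Analysis Populations, limit the ITT statement to efficacy and the Table 5 comparison, and add a safety set for Table 4: participants who received at least one study session, grouped by treatment received. Use the number in that set as the Table 4 column heading. Table 4 lists needle phobia, which could arise before a first session, so the definition should say where such cases are counted.

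Because this set does not deal with partial exposure, also report sessions delivered and events per 100 sessions by arm. In the combined arm, count CAT and CAE sessions separately, since needling events can arise only from the former. The protocol's Data Management section already has the case record form recording each participant's treatment, so no new data are needed.

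Keep ITT for Table 5. A treated-set version of that table should be supportive at most.

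The cost is one definition, a changed denominator and a little extra tabulation. The Table 4 percentages may become slightly less favourable.

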## **Plan of Investigation**

### Design

This is an assessor-blinded, randomized controlled trial. A total of 248 eligible subjects will be recruited from local nursing and care homes. They will be randomly assigned to either an acupuncture group (named the “comprehensive acupuncture therapy [CAT]” group), an acupressure group (named the “Comfy Acupressure for the Elderly [CAE]” group), a combined acupuncture and acupressure group (named the CAT+CAE group), or a control group (named the routine care group), with 62 subjects per group. Subjects assigned to the CAT, CAE, and CAT+CAE groups will respectively receive 2 sessions of CAT, 3 sessions of CAE, and a combination of both per week for 12 weeks. The primary outcome is the baseline-to-endpoint change in score of the Montreal Cognitive Assessment

(MoCA). Secondary outcomes include various domains of MoCA, functional independence, psychological well-being, sleep quality, and level of pain. A generalized linear mixed-effect model will be used to compare outcomes over time among the four groups. This trial has been approved by the Institutional Review Board of the University of Hong Kong/Hospital Authority Hong Kong West Cluster (Ref No.: UW 19-821). The study protocol has been registered at ClinicalTrials.gov (NCT04305951) before enrolment. The trial will be conducted in compliance with the protocol, the ethical principles of the Declaration of Helsinki and its subsequent amendment. The study flow chart is shown in [Figure 1](#).

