### **Data processing and analysis**

One biostatistician who is blinded to interventions will be responsible for statistical analysis. The analysis will be carried out on the intention-to-treat (ITT) population, for which participants have been randomized. A linear mixed-effect model will be applied to compare the primary outcome (changes in total MoCA score from baseline) and secondary outcomes (changes in scores of the Digit span test, MBI, VAS, GDS and ISI), with time (baseline, week 6, and week 12) and group (CAT, CAE, CAT+CAE, and routine care) as categorical fixed factors and random intercepts within a scaled identity covariance matrix. Gender, age, baseline MoCA score, and baseline medication will serve as covariates. Subgroup analysis will be further conducted to compare outcomes by gender, age, and severity of dementia to detect whether these factors are associated with the outcomes. Pairwise comparisons will be further carried out to examine between-group differences. One-way analysis of variance (one-way ANOVA) will be used to detect differences in continuous baseline variables. Categorical baseline variables, including discontinuation and incidence of AEs, will be analyzed using the Chi-square test or Fisher's exact test. Statistical significance was defined as a two-tailed  $P < 0.05$ . The analysis will be conducted using R Studio software.

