- (a) Routine care: All participants in the four groups will continue their current routine care and medications as usual. These routine cares will serve as covariates included in outcome analysis.
- (b) CAT regimen: Subjects assigned to the CAT group will receive CAT treatment in addition to routine care. CAT will be conducted for 2 sessions per week for 12 consecutive weeks. Details of selected acupoints and treatment procedures can be found in the study protocol.
- (c) CAE regimen: Subjects assigned to the CAE group will receive CAE in addition to routine care. CAE interventions will be conducted 3 times per week for 12 consecutive weeks. The detailed procedure for CAE is summarized in the study protocol.

(d) **CAT+CAE regimen:** Subjects assigned to the CAT+CAE group will receive CAT+CAE in addition to routine care. The procedure is a combination of CAT and CAE as described above.

Study outcomes

Primary outcome

The primary outcome will be evaluated by the mean change of the Montreal Cognitive Assessment (MoCA) score between baseline and endpoint. The MoCA test assesses seven domains of cognitive function, including visuospatial, naming, attention, language, abstraction, recall, and orientation domains, for a total possible score of 30 points.³⁻⁴ Assessments will be conducted at baseline, week 6, and week 12.

Secondary outcomes

Assessments will be conducted at baseline, week 6, and week 12.

The secondary outcomes will include:

- (a) the Digit span test for attentional function, short-term memory, and working memory, including the Digit Span Forward (DSF) and the Digit Span Reverse (DSR);⁵
- (b) the Modified Barthel Index (MBI) for functional independence;⁶⁻⁷
- (c) the Visual Analogue Scale (VAS) for pain;⁸
- (d) the 15-item Geriatric Depression Scale (GDS-15) for depression;⁹⁻¹⁰ and
- (e) the Insomnia Severity Index (ISI) for insomnia.¹¹

Safety outcomes

The severity of adverse events (AEs) will be assessed according to the Common Terminology Criteria for Adverse Events (CTCAE) v5.0 criteria.¹² AEs will be systematically recorded, in which AEs that first appear in the study or worsen relative to the pre-study status will be recorded at each visit, including date and time of onset, duration, severity, relationship to intervention, and action taken accordingly. The causality between treatment procedures and AEs will be assessed.

Sample size determination

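### The primary model keeps baseline as a time level for a change score and names no group-by-time term or visit: read literally it understates the Week-12 effect, and extended to fill Table 2 it can understate the standard error

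*SAP*

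**What the plan says.** The SAP (Primary outcome) fits a linear mixed model to "compare the primary outcome (changes in total MoCA score from baseline), with time (baseline, week 6, and week 12", with the four groups as the other factor. Both enter "as categorical fixed factors and random intercepts within a scaled identity covariance matrix". Gender, age, baseline MoCA and baseline medication are covariates, and pairwise group comparisons follow with no visit named.

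The Protocol (Data processing and analysis) specifies the same model: "with time (baseline, week 6, and week 12) and group (CAT, CAE, CAT+CAE, and routine care) as categorical fixed factors". Its Design section describes it more loosely: "A generalized linear mixed-effect model will be used to compare outcomes over time among the four groups". Neither document writes a group-by-time term.

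Other parts of the plan ask for more than main effects can supply:

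- SAP, Study outcomes: "The primary outcome will be evaluated by the mean change of the Montreal Cognitive Assessment (MoCA) score between baseline and endpoint".
- SAP, Proposed Table 2: separate Week-6 and Week-12 differences for all six pairs of groups, with P values taken from a baseline-adjusted mixed model.
- SAP, Secondary outcomes: the same construction, for "changes in scores of the Digit span test (DSF and DSR), MBI, VAS, GDS and ISI, with time (baseline, week 6, and week 12". The covariate list is again "Gender, age, baseline MoCA score, and baseline medication will serve as covariates", so a secondary outcome's own baseline is not listed.

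**The concern.** A change score at baseline is 0 by construction and has no variance. A random-intercept model with one residual variance treats those rows as if they were as variable as the rows at Weeks 6 and 12. What this does depends on which term is reported, and the plan does not say.

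With main effects only, the zeros enter the estimate and pull the group difference towards zero. With group-by-time added, they leave the Week-12 estimate alone but dilute its variance. The first reports a quantity that is not the endpoint change. The second gives a P value that is too small and a confidence interval that is too narrow. Both affect the primary analysis, and the same wording governs every secondary outcome.

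**Working it through.** **Inputs.** From the documents: 62 per arm, four arms, SD of change 3.6, difference 2.1, two-sided 5%. Assumed, because the documents do not give them: visit SD 5, correlations between visits or between changes as stated below, and complete data.

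**1. The plan's own figure.** n = 2/(2.1/3.6)² × 7.9 = 46.4, and 46.4/0.75 = 61.9, so 62 per arm reproduces. The true standard error of a Week-12 difference between two arms of 62 is then 3.6 × √(2/62) = 0.647.

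**2. The model as literally written (main effects only).** In complete data the group coefficient estimates (0 + d6 + d12)/3, where d6 and d12 are the true group differences in change. For d12 = 2.1:

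| d6 | Estimate | Share of d12 |
|---|---|---|
| 2.1 | 4.20/3 = 1.40 | 67% |
| 1.05 | 3.15/3 = 1.05 | 50% |
| 0 | 2.10/3 = 0.70 | 33% |

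In simulation (correlation between the two changes 0.3 to 0.8) the reported standard error was right for this pooled quantity (ratio 0.99 to 1.01) and type I error was 4.9% to 5.2%.

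**3. Group-by-time added, baseline rows kept, Week-12 difference read off.** The model's variance at any visit is the average over the three visits, (0 + v6 + v12)/3, where v6 and v12 are the variances of change. The true variance is v12. With k = v6/v12 and no covariates:

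- reported SE / true SE = √((1 + k)/3)
- type I error = 2[1 − Φ(1.96 × ratio)]

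| k | SE ratio | Type I error |
|---|---|---|
| 0.5 | 0.71 | 17% |
| 0.64 (Week-6 SD 0.8 of Week-12 SD) | 0.74 | 14.7% |
| 1 | 0.816 | 11.0% |
| 1.25 | 0.87 | 9% |
| 2 | 1.00 | 5% |

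At k = 1 the reported standard error is 0.816 × 0.647 = 0.528.

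Simulation with equal SDs, with and without baseline MoCA as covariate, gave ratios of 0.81 to 0.83 and type I error of 10.4% to 11.3%. With a baseline-change correlation of −0.5 it gave 0.845 and 9.9%. The Week-12 estimate for a true 2.1 averaged 2.10, so it is unbiased.

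With visit SD 5 and correlation 0.74 between all visits, the SD of change is √(2 × 25 × 0.26) = 3.6. Type I error with the baseline covariate was then 10.3%. If the correlation with baseline is instead 0.83 at Week 6 and 0.74 at Week 12, v6 = 2 × 25 × 0.17 = 8.5, v12 = 13 and k = 0.65. The closed form gives 14.6%, and simulation with the covariate gave 13.1%.

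**4. Same model, Week-12-minus-baseline contrast.** Let r be the correlation between the two changes. Reported/true variance is 2(1 + k − r√k)/3. Equal correlation of raw scores implies k = 1 and r = 0.5, so the ratio is 2 × 1.5/3 = 1 and type I error is 5.0%. At k = 1, r = 0.3 gives 3.7% and r = 0.9 gives 9.3%. Under the decaying correlation of step 3, simulation gave about 8%.

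**5. Baseline rows removed.** With change at Weeks 6 and 12, group-by-visit and equal SDs, the Week-12 estimate is 2.10, the SE ratio 1.00 to 1.01 and type I error 4.8% to 4.9%.

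**The case against.** The strongest reply is that the 10–11% belongs to a model the SAP does not write. That is correct. A reader might infer that the primary test, as specified, has an 11% error rate. The documents do not support this: without the interaction there is no Week-12 difference to read off, and the single pooled test holds its level at about 5%. The literal fault is understatement of the effect.

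A second reply is that listing three time levels points to the Week-12-minus-baseline contrast, which matches the outcome definition. Under equal correlation of raw scores that contrast is about nominal. This also stands, but the contrast is not named, and its level moves with correlations that the documents do not give.

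Third, one might say the inflation in step 3 holds whenever k is below 2. That break-even applies only without covariates. Once baseline MoCA is in the model, the adjusted baseline rows are no longer constant, and the break-even falls somewhat below 2.

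Fourth, raw MoCA may have been intended. While baseline MoCA stays a covariate, raw and change responses differ only by a shift in its coefficient, so the group contrasts are identical and this does not help.

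Finally, a reader might infer scope for choosing the favourable contrast after seeing the data. The SAP blinds the biostatistician, bars analysis before SAP approval and shows both visits for every pair, so the documents give no ground for suspecting that. They still do not determine which P value is primary.

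**Conclusion.** The point holds in a limited form. The model text and Table 2 cannot both be followed.

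- **Literal reading:** a valid test at about 5%, but an estimate one third to two thirds of the Week-12 difference if the Week-6 effect lies between 0 and the Week-12 effect.
- **Interaction added, baseline rows kept, Week-12 difference reported:** an unbiased estimate, a standard error about 0.82 to 0.85 of the true value, and type I error about 10–11% with equal SDs of change and complete data. If the variance of change grows from Week 6 to Week 12, the error is higher, about 13–15% under the assumed decay.
- **Week-12-minus-baseline contrast:** about nominal under equal correlation of raw scores, about 8% under that decay.

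The wording defect is certain. Confidence in the sizes is moderate, because visit SDs, correlations and dropout timing are all assumed. Since this is the primary analysis, it should be settled before any data are analysed.

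**What to change.** In the SAP (Primary outcome, Secondary outcomes) and the Protocol (Data processing and analysis), remove baseline from the levels of time and specify:

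- Response: change at Weeks 6 and 12.
- Fixed effects: group, visit, group × visit, baseline value of the outcome, age, gender, baseline medication.
- Covariance: unstructured for the two visits, fitted by REML, in place of the random intercept.
- Primary estimate: group difference in MoCA change at Week 12.

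For each secondary outcome, use its own baseline as covariate.

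An acceptable alternative is raw MoCA at all three visits with an unstructured covariance, no baseline covariate, and the group difference in Week-12-minus-baseline change as the named contrast.

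Two smaller wording points can be aligned in the same edit: the model name in the Protocol's Design section, and the sentence under Routine care, "These routine cares will serve as covariates included in outcome analysis", which does not match the covariate list.

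The cost is wording and a few lines of code. P values will be less favourable than under the interaction reading with baseline rows kept. Participants with no post-baseline score add nothing to the change model, so their number should be reported by arm. The 62 per arm is unaffected.
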